Results: NETT participants improved on the social behavior composite capturing nonverbal communication, social relations, and empathic responding skills at endpoint compared to controls ($B=-.31$, $SE=.14$, $p=.04$). No group differences were found on the social cognition composite ($B= 0.00$, $SE=.13$, $p=.98$). Outcomes at a three-month follow-up interval were not significant suggesting a potential waning effect of the CBI intervention over time ($B=-.14$, $SE=.19$, $p=.47$). Moderator analyses indicated higher verbal IQs were associated with social behavior improvements in NETT but not controls ($B=-.02$, $SE=.01$, $p=.03$). Results also show improvements on low-intensity (i.e. more ambiguous) facial emotion identification items in NETT but not controls (estimate =1.1, $p<.01$, Cohen's $d = .56$). Poor quality data and compliance issues limited the imaging sample to approximately

Confidential

Rush University Medical Center

half of the behavioral data. In this subset of participants, NETT increases activation in mentalizing regions including the medial prefrontal cortex and temporal pole junction during an averted eye gaze task (Figure 2)⁵⁰.

Summary: Our findings demonstrate short-term, specific treatment effects of targeted CBI-based SST curricula of NETT on core social-communication behaviors in youth with ASD. The limited effects on social cognitive processes are supported by two recent Cochrane reviews^{14,51}.

Intranasal oxytocin for the treatment of children and adolescents with autism spectrum disorder

ClinicalTrials.gov lists 22 clinical studies of intranasal oxytocin (IN-OXT) in ASD which are actively or recently completed recruitment. Of the handful of published findings in this area, the vast majority include small single-dose challenge studies in adults with ASD. Studies suggest a medium effect size on measures of social cognition and social impairment⁴¹. Overall, IN-OXT was well-tolerated and had a side effect profile including restlessness, increased energy, and increased irritability. The PI and collaborators published on a modified maximum dose-finding and safety study of a 12-week oxytocin daily monotherapy in verbal, youth with ASD⁵². The highest dose evaluated was .4 IU/kg/dose and was well-tolerated. Several measures of social behavior, repetitive behavior, and social cognition demonstrated change at endpoint (12 weeks) as well as at a 3-month follow-up post-discontinuation of IN-OXT⁴⁰.

2. Study Aims

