8.8. Statistical analysis

Specific Aim 1 & Exploratory Aim 1: Safety and tolerability will be analyzed by analyzing for group differences on total scores and domains of the AE form and satisfaction surveys respectively. Efficacy analysis will be follow analytic procedures used to derive social behavior and social cognition composites for the Seaver-NETT RCT¹⁶. First, a principal components analysis with varimax (orthogonal) rotation will be conducted on subscales of the primary social behavior measures - Griffith Empathy Scale and CCC-2; and raw total scores on primary social cognition outcomes – RMET and DANVA2. The PCA is used to develop composite scores in a field with no viable outcomes for higher-order core social impairments as well as to minimize floor and ceiling artifacts, effects of variability in response, and other sources of measurement error. Variables with high factor loadings for subscales will be entered into composite score development for the social cognition and social behavior composites. Missing, invalid, and/or incomplete data (i.e. more than 30% items missing when not pre-defined by scale) will be excluded from the factor analysis.

A linear mixed model analysis will be conducted on all participants with at least two of four available time points (Wk 0, Wk 12, 1-mon, 3-mo). Composite scores of co-primary outcomes social behavior and social cognition will be used as the response variable; treatment condition, time, and condition * time interactions will be covariates. Verbal IQ will also be entered into the model in exploratory moderator analyses. We will estimate effect sizes (Cohen's d) and confidence intervals (95%) acknowledging the likelihood that analyses may not permit definitive conclusions given the likely size of the confidence intervals.

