8.9. Sample size considerations

Based on data from the NETT trial, published trials in sustained OT treatment⁵⁴, and single-dose challenge studies in autism⁴⁹ we expect our sample size (n=25/group with 5% attrition) to yield 80% power to detect a difference in means of 0.40, assuming a standard deviation of differences of 0.670, with a 0.050 two-sided significance level. Although potentially underpowered, we believe data from this trial will provide important information on safety, tolerability, and treatment targets from a novel, multi-dosing OT-combined treatment strategy. Specific Aim 2 (treatment targets, pre-treatment factors predictors). Repeated measures ANOVAs will be conducted to evaluate group differences on social behavior and social cognition composites, social recognition, mental state inference, affiliation, social reward and social competence (i.e. SSIS) in order to identify potential treatment targets for the combined treatment approach. Factors predicting treatment response will include global scores on all baseline measures. Responder status will be entered as a categorical variable as defined above (CGI-I≤2 + SSIS > 25%). PCA will be conducted on significant baseline predictors to develop composite variables and used to predict response using logistic regression.

Confidential

Rush University Medical Center

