Prior to the PCAs, missing, invalid, and/or incomplete data will be removed. For SBI, observations missing one or more items on either CCC-2 subscale and/or greater than 30% of GEM items will be removed. For SC, observations with less than 50% of the responses (due to administrative error) on the RMET and/or DANVA2 will be removed. Provided these measures have high and near comparable component loadings on a single factor for each domain, thus confirming previous findings, they will be combined for separate composite scores for social behavior impairment (SBI) and social cognition (SC). To create the SBI composite score, total score on the GEM is reversed so that the higher scores reflect greater impairment as on the CCC-2. To create the SC composite score, percent correct was calculated for the RMET and DANVA-2 since they differ in total number of items and to adjust the denominator when all items were not presented due to administrative error. Subsequently, for each measure, scores will be standardized using the sample mean (and standard deviation) at baseline to account for change from baseline analyses, different and wide ranges of scores, and to ensure that composite scores across domains can be easily compared on the same scale (i.e., z-score). Following outlier detection (see below), standardized scores for each domain (SBI, SC) will then be averaged together to generate final composite scores at each time point. As such, a change in composite score reflects a change from baseline.

Outlier Detection. Individual scores from measures that are either influential points or outlier values (i.e., based on Cook's distance $> .5$ and/or Bonferroni-corrected outlier based on r-student residuals, respectively) and plausibly invalid (e.g., due to clinical reasons or administrative errors) will be removed. Composite scores will then be re-standardized and remaining extreme outliers (>3 SD above the mean for a specific timepoint) will be removed if they change the model significantly ($>10\%$ change in estimated values).

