Data Analysis. Primary: Composite scores of both primary outcomes (i.e., SBI and SC) will be used as the response (i.e., outcome) variable in a series of mixed-effects linear regression models using the *lmer* package in *R Studio* to assess the effect of treatment condition (ION-ASD vs. Facilitated Play), time (e.g., change from baseline after 12 weeks), and condition X time interaction. Across all models, the individual participant will be included as the random effect. Age, verbal IQ, ADHD and generalized anxiety (from the Child & Adolescent Symptom Inventory-5 [CASI-5] T-scores) will be entered into the model to be examined as potential covariates and/or moderators to outcomes as in prior work. We will estimate effect sizes (standardized Betas) and confidence intervals (95%) acknowledging the likelihood that analyses may not permit definitive conclusions given the likely size of the confidence intervals. Finally, if the statistical assumptions of the model are not met (e.g., homoscedasticity, normality, linear relationships), generalized linear models with appropriate link functions or potential transformations of predictor variables will be assessed.

Secondary Outcomes. The linear mixed-effects models will also be used on secondary outcome measures: SRS T-score, mean Caregiver Strain Global rating scale. Responder (i.e., Clinical Global Inventory-Improvement [CGI-I]) analysis will be conducted using either a Chi-squared or Fisher's exact test (when observations are small such that $>20\%$ of cells have *expected* count <5) on the number of responders (i.e., CGI-I scores of 1-2) versus non-responders (i.e., CGI-I scores of 5-7) by group.

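### The primary model leaves the baseline composite as a response with a free mean in each arm and does not adjust for it, so the Week 12 effect is unbiased but usually less precise than the same data allow

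*SAP*

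**What the plan says.** The SAP (Data Analysis, Primary) makes each composite the response in mixed linear models "to assess the effect of treatment condition (ION-ASD vs. Facilitated Play), time (e.g., change from baseline after 12 weeks), and condition X time interaction". Its random part is one sentence: "Across all models, the individual participant will be included as the random effect". Age, verbal IQ, ADHD and generalized anxiety "will be entered into the model to be examined as potential covariates and/or moderators to outcomes as in prior work".

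Protocol section 8.8 gives the same structure: "treatment condition, time, and condition * time interactions will be covariates". It analyses "all participants with at least two of four available time points (Wk 0, Wk 12, 1-mon, 3-mo"), so Week 0 is one of the response rows.

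Neither document lists the baseline composite as a covariate or gives the two arms a common baseline mean. The SAP does use baseline for scaling: "scores will be standardized using the sample mean (and standard deviation) at baseline". That is a linear rescaling applied to everyone, not an adjustment. The SAP re-standardises the composites after outlier removal but does not say to which mean and SD.

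**The concern.** With a condition main effect and Week 0 among the responses, each arm has its own baseline mean. The Week 12 condition-by-time term is then the difference between arms in mean change from baseline. Reading the SAP's phrase about change from baseline as a change-score response gives the same contrast.

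Randomisation already makes the true baseline means equal. Estimating them separately carries chance baseline differences into the effect estimate at full weight, whereas adjustment carries them at the weight the data support.

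What is at stake is interval width. Both documents expect confidence intervals that may be too wide for firm conclusions, and section 8.9 concedes that the trial may be underpowered. A narrower interval from data already planned would address that directly.

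**Working it through.** **Inputs.** From protocol 8.9: difference 0.40, two-sided 0.05, 25 per group with 5% attrition, 80% power, "assuming a standard deviation of differences of 0.670". From protocol 3.1: 70 children in Phase 2 at 1:1, so 35 per arm. From protocol 1.1: the prior trial enrolled 69 and reports a social behaviour effect "at endpoint compared to controls ($B=-.31$, $SE=.14$, $p=.04", with an SE of .13 for social cognition. Not in the documents: rho, the baseline to Week 12 correlation of the composite, and the composite SD, S. S is assumed to be 0.8-1.0, because an average of baseline z-scores has SD below 1 unless they are perfectly correlated.

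**1. The plan's own figure.** 25 less 5% is about 24. A one-sample (paired) t-test has noncentrality 0.40/(0.67/√24) = 2.92 and power 79.98%, which matches the stated 80%. A two-sample t-test at 25 per arm gives 54.3%. So 0.67 behaves as the SD of a child's change, and it is used below as the within-arm SD of change, SDc.

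**2. Variances, equal SDs at both visits.**
- Planned contrast: (2/n) × 2S²(1−rho).
- Baseline-adjusted or constrained: (2/n) × S²(1−rho²).
- Ratio, adjusted to planned: (1+rho)/2.

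Exact generalised least squares with four equally correlated visits gave 0.65, 0.75, 0.85, 0.90 and 0.95 for rho 0.3, 0.5, 0.7, 0.8 and 0.9, as the formula predicts. In simulations with a true effect of 0.40 and 25 per arm, both estimators averaged 0.40 (0.399-0.403), so neither is biased.

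**3. Size with SDc = 0.67.** rho = 1 − SDc²/(2S²). The cost of estimating the baseline slope multiplies the ratio by 1 + 1/(N−4), which is 1.015 for N = 70. At 35 per arm:

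| S | rho | ratio | net ratio | 95% half-width | power for 0.40 | equivalent extra children per arm |
|---|---|---|---|---|---|---|
| planned | – | 1 | 1 | 0.320 | 0.692 | – |
| 0.8 | 0.649 | 0.825 | 0.837 | 0.292 | 0.767 | 6.8 |
| 0.9 | 0.723 | 0.861 | 0.875 | 0.299 | 0.749 | 5.0 |
| 1.0 | 0.776 | 0.888 | 0.901 | 0.303 | 0.737 | 3.8 |

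The last column is 35/(net ratio) − 35. At 25 per arm the half-width falls from 0.381 to 0.350-0.363 and power rises from 0.543 to 0.584-0.615. Over both sizes the net power gain is about 4 to 7.5 points.

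**4. Size with the prior trial's SEs.** If those are unadjusted change contrasts in near-equal arms (not stated), SDc = SE × √69/2, which is 0.540 for .13 and 0.581 for .14. Net ratios at 35 per arm are 0.900-0.941 (0.54) and 0.882-0.930 (0.58), a saving of about 6-12%. Power rises from 0.863 to 0.883-0.896 and from 0.812 to 0.839-0.857. Over 25 and 35 per arm the gain is about 2-5 points. Section 1.1 restricts that analysis to children with at least two visits, so 69 is an upper bound. A smaller number would lower SDc and the saving.

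**5. Unequal SDs.** rho = (S² + SD12² − SDc²)/(2 × S × SD12), where SD12 is the Week 12 SD, and the ratio is SD12²(1−rho²)/SDc². With SD12 15% above baseline it is 0.949-0.991 (SDc 0.67) or 0.980-1.000 (0.54-0.58). After the 1.015 slope cost, this runs from a saving of about 4% to a loss of about 2%. With SD12 15% below baseline it is 0.658-0.722, a gross saving of 28-34%.

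**6. The listed covariates.** In complete data, a time-constant main effect cancels from a within-child contrast. In one simulated two-visit data set at 35 per arm, the condition-by-time estimate was 0.3566 with SE 0.1585, both without and with four predictive main-effect covariates.

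**The case against.** The strongest reply is that this is a preference about efficiency. The trial is a proof-of-concept pilot that reports estimates with intervals and admits they may be inconclusive. The planned contrast is valid, conventional and continuous with the prior trial. This stands, and it is why the point is a recommendation and not a repair.

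The size is also uncertain. rho and the composite SD are assumed, and the SD of change is either a reading of section 8.9 or a back-calculation on conditions that section 1.1 does not state. If re-standardisation gives the final composite a baseline SD of 1.0, only the smallest saving in each range applies. These objections stand too. They limit the size but do not change its direction when the SDs are similar.

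The covariate argument covers main effects in complete data. The SAP also allows moderators, and section 8.8 admits children with two of four visits, so some baseline information could enter by those routes. Neither route is specified as an adjustment for the baseline composite.

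A reader might go further and infer that the random-intercept model gives a wrong standard error. That depends on whether the four visits are fitted together and on correlations between visits that the documents do not give. It is a separate question and is not claimed here.

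**Conclusion.** The point holds as a modest loss of precision. With equal SDs at both visits, the planned Week 12 contrast has 2/(1+rho) times the variance that the same data allow. For an SD of change of 0.67 and a composite SD of 0.8-1.0, adjustment saves about 10-16% net at 35 per arm. If the composite's baseline SD is 1.0, the saving is about 10%, worth roughly 4 children per arm. For an SD of change of 0.54-0.58 the saving is about 6-12%. If the Week 12 SD is clearly above baseline, there is no useful gain.

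Two stronger inferences are not supported. First, a reader might conclude that omitting the baseline covariate biases the effect. Under randomisation it does not. Second, a reader might blame this choice for the gap between the stated 80% power and the 54.3% of a two-arm comparison with the same inputs. That gap comes from the form of the sample size calculation. At 25 per arm and an SD of change of 0.67, adjustment recovers only about 4-7 points of it.

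**What to change.** In the SAP, name the Week 12 condition difference as the primary estimate for each composite, with time categorical, and choose one of two forms:

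- **Baseline as covariate**, with post-baseline visits as responses. This drops children whose baseline composite is missing or removed, unless it is imputed.
- **Constrained longitudinal model**, with all visits as responses and one common baseline mean. This keeps those children.

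In either form, use an unstructured within-child covariance with Kenward-Roger degrees of freedom. A robust SE is acceptable only with a small-sample correction: an uncorrected sandwich SE with a normal reference rejected a true null in 6.5% of simulated trials at 25 per arm and 5.6% at 35.

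Do not simply delete the condition term from the random-intercept model. If the Week 12 SD is 15% above baseline, the model SE is 0.937 of the true SE and type I error is 2 × [1 − Φ(1.96 × 0.937)], about 6.6%.

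State the basis of the re-standardisation, and keep the prior-trial-style model as a sensitivity analysis.

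The cost is SAP wording and a different R function (mmrm, for example), with no new data or visits. The downsides are more covariance parameters in a small sample (10 with four visits as responses, 3 with two) and a departure from the prior trial's primary model.

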3.1. Study Design

This is a two-phase, 3 year, randomized, single-blind, parallel group, contact controlled pilot trial of OXT augmentation of CBI groups in youth with ASD. Phase 1 (n=10) is an initial development trial to refine manuals, procedures, and outcome evaluations. Phase 2 (n=70) will evaluate feasibility, safety, and preliminary efficacy of ION-ASD relative to the contact control (i.e. social play group). All participants are expected to be outpatients and will participate in a 12-session group therapy, with a follow-up study visit at 24 weeks. Evaluations will be conducted at four time points: Screening, Baseline, Endpoint (week 12), and Follow-up (1-month & 3-months post-treatment).

Each phase will randomly assign in a 1:1 ratio to either ION-ASD or control in blocks of 10. Efficacy outcomes will be evaluated by both caregiver report and blinded independent evaluators (IE); safety assessments will be conducted by unblinded treating medical clinicians (Medical TC). Caregivers and participants will be instructed to conceal group assignment from IEs. IEs, participants, and caregivers will also be instructed on reporting strategies should group assignment be revealed. Corrective action plans in these scenarios will be employed if necessary and include changing IE raters and flagging data. IEs will be asked to “guess” patient conditions at the end of the trial to evaluate integrity of the blind.

Medical TCs will monitor side-effects using weekly ratings with the participant and caregiver. Clinical IEs will evaluate global functioning and social communication skills. Neurocognitive IEs will conduct blinded neurocognitive assessments (see Appendix A: Time & Events Schedule).

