Oxytocin will be administered in an intranasal format using the synthesized peptide oxytocin in a solution formulated to promote absorption through the nasal mucosa. Intranasal oxytocin (OXT) will be administered at a dose of 24 IU (3 puffs per nostril), four times per week during the 12-week intervention. The first dose will be administered before the group session at week 1. One administration will occur 30 minutes prior to the weekly social skills group therapy session, and the other three administrations will occur 30 minutes prior to at-home homework/practice sessions. Parents and participants will undergo training modeled after SOARS-B procedures (e.g. parent medication administration handout, in-vivo practice with placebo). If groups are conducted virtually, medication will be mailed to families. Regardless if the group is virtual or in-person participant and guardian will be required to meet with study physician and study PI to review how to properly administer the medication. This review can occur virtually, if needed.

Control Condition: Facilitated Play

The facilitated play condition was manualized for use in the R21 and is a child-directed social play group. Therapists tailor available activities based on interests and abilities of group members. Standard educational practices for children with ASD including visual supports, schedules, and short-directed statements are also used. The concurrent parent group is supportive in nature. Groups will be led by doctoral level clinicians trained in eclectic therapeutic approaches (e.g. supportive psychodynamic). The treatment manual described methods to tailor child-directed play based on the interests and abilities of group members. Therapists established "stations" to support object play (e.g. legos, board games), motor/tactile (e.g., drawing), and dramatic play. The treatment manual also provided instruction on use of reflective statements to foster communication with the child and between peers. Each group session began with a review of a posted visual schedule, a check-in circle, activity-time, and wrap-up. The 30-minute concurrent parent group was supportive in nature and facilitated by the lead therapist.

Confidential

Rush University Medical Center

[figure not shown]

Figure 3. ION: Weekly study procedures

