5.2. Study Procedures

Screening Visit(s)

Participants and their parent(s)/legal guardians will come in to sign informed consent and meet with a study clinician to establish eligibility. The following measures will be obtained: a diagnostic assessment, including the ADOS-2 (if required) and DSM-V interview, the ADI-R (if required), a cognitive assessment (WASI-II, KBIT, or WISC-V, if required), the ABC, the CGI-S (Global and Social), the AE rating form, height, weight, vital signs, temperature, a physical examination, review of medical and psychiatric health and concomitant therapies, and a pregnancy test (if applicable). The ADOS-2 (if required) will be video recorded. The screening visit is anticipated to take approximately 4-6 hours to complete. The visit can be split into two visits if this is better for the participant and may be combined with the baseline visit to facilitate scheduling and compliance with visit windows. If required, the following measures can be completed virtually: consenting, DSM-V interview, ADI-R, CARS2, the ABC, the CGI-S (Global and Social), the AE rating form, review of medical and psychiatric health and concomitant therapies.

ECG and safety lab assessments will be completed no more than 30 days before the first dose of medication is administered.

In addition, a physical exam will be conducted, and height, weight, temperature, and vital signs will be obtained. At the baseline visit, the participant will also be randomized to receive either ION-ASD or control (social play), and the research pharmacy will be notified by research staff to dispense a two week supply of study drug to families assigned to ION-ASD. Blood work will be collected prior to participants taking their first dose of study medication. The randomization form will be developed prior to screening/recruitment for each cycle and present randomization schema for 10-12 participants each time. Coordinators will open the Randomization form after the completion of baseline assessments.

Screening and baseline procedures may be combined to accommodate participant schedules.

Baseline Visit(s)

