Participants entering the study will undergo the baseline assessments, which are anticipated to take approximately 6-10 hours to complete no more than 21 days from the last screening visit. The visit can be split into as many as three visits if this is better for the participant. The following measures will be completed: the CGI-S (Global and Social), AE rating form, the RMET, the CASI-5, the RBS-R, the SRS, the BASC-3, the PDDBI-SV, the Griffith Empathy Scale, the Children's Communication Checklist, the Caregiver Strain, the DANVA2, the TAT, and the Test, GEMEP emotion recognition test, and sensor-based social-communication monitoring tests..

Vineland Scales of Adaptive Functioning (3rd edition): The VABS-3 is a survey administered to a parent or caregiver is organized around four Behavior Domains: Communication, Daily Living Skills, Socialization, and Motor Skills. The VABS-3 will take the parent/caregiver/LAR approximately 20-60 (average 30) minutes to complete, depending on the subject's age and level of functioning.

Weekly Visits (1-11)

Interventions are delivered in 12-session modules occurring on a weekly basis. Groups will commence when all participants in a cycle have completed baseline evaluations and within 21 days of participant's last baseline visit. Participants will receive group treatment conditions as described in Section 5.1 (Treatment Conditions). Participants randomized to ION will also be prescribed 24 IU (3 puffs/nostril) of intranasal oxytocin 4 times/week to be administered by the parent 30-minutes prior to homework practice (3 x/week) and 30 minutes prior to each weekly group session.

Safety ratings during group: Weeks 1, 3, 5, 7, 9, 11 (or biweekly schedule depending on group start day/date)

Vital signs, temperature, and AE ratings will be completed in 6/12 sessions by a licensed physician on participants in all groups. In addition, the CGI-I (Global and Social) will be completed by the Study clinician. At

Confidential

Rush University Medical Center

Week 6, the CY-BOCS, the CASI-5, the RBS-R, the PDDBI-SV, the Griffith Empathy Scale, the Children's Communication Checklist, the Caregiver Strain and the ABC will be completed. In addition, a two week supply of study drug will be dispensed at weeks 1, 3, 5, 7, 9, 11. Unplanned visits will be permitted if there are any concerns about AEs. Safety visits are expected to take 15-20 minutes.

Week 6 (Midpoint)

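### Both arms are treated in therapy groups formed by cycle, but the participant is the only random effect and no group-level analysis is planned, so the 95% intervals may be too narrow

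*SAP*

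**What the plan says.** Delivery is by group in both arms. Protocol 3.1 says participants "will participate in a 12-session group therapy", and Protocol 5.1 describes child and parent groups for ION-ASD and for facilitated play. In the play arm, "Therapists tailor available activities based on interests and abilities of group members", and "The 30-minute concurrent parent group was supportive in nature and facilitated by the lead therapist".

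Groups are formed by cycle. Protocol 5.2 says "Groups will commence when all participants in a cycle have completed baseline evaluations". Each phase "will randomly assign in a 1:1 ratio to either ION-ASD or control in blocks of 10" (3.1), and the form prepared for each cycle is to "present randomization schema for 10-12 participants each time" (5.2).

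The analysis does not carry this structure. The SAP, under Data Analysis, says "Across all models, the individual participant will be included as the random effect". The fixed effects in Protocol 8.8 are condition, time and their interaction. The SAP adds age, verbal IQ, ADHD and generalised anxiety as candidate covariates or moderators. The assumption checks it gives as examples are equal variance, normality and linearity, not independence. The promised output is standardised effects with 95% intervals. Neither document mentions an ICC, a design effect, a robust variance or a cluster-level sensitivity analysis.

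**The concern.** Children are randomised individually, and the therapy groups exist only from the start of treatment. Anything that makes members of one group change alike (the therapist, the peers, the parent group, activities fitted to that group) therefore acts on change from baseline. A participant intercept absorbs stable differences between children, not a shared shift in change. The model then treats the children in one group as independent pieces of information about the treatment effect.

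The protocol's own rationale makes some shared change plausible. It expects benefit partly through environmental contingencies such as parent training (section 1), and it describes the play group in the earlier NETT trial as a control for therapist training, peer exposure and parent engagement (1.1).

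The case differs between the two primary composites. It is stronger for social behavior, which caregivers rate while attending a shared parent group. It is weaker for social cognition, which is tested directly in the child: "Neurocognitive IEs will conduct blinded neurocognitive assessments".

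What is at stake is whether the reported precision can be trusted when a later trial is planned.

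**Working it through.** **The plan's own figure.** Protocol 8.9 claims 80% power for a difference of 0.40, SD of differences 0.67, 25 per group with 5% attrition. A one-sample or paired t-test with 24 evaluable gives noncentrality 0.40/0.67 × √24 = 2.92 and power 0.800, so the figure reproduces in that form. As a two-sample t-test with 25 per arm the power is 54%. That mismatch is a separate matter. Here it shows only that the figure makes no allowance for clustering, and that using 0.67 below as the between-child SD of change is an assumption.

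**Inputs.** From the documents: Phase 2 n = 70, 1:1, blocks of 10; 10-12 children per cycle form. Assumed: one group per arm per cycle, hence 70/10 = 7 cycles and 5 children per group (6 at the upper end of the form). Sizes 3 and 4 are included because attrition (8.9), removal of unusable observations (SAP, Data Reduction) and the two-time-point requirement (8.8) can only shrink the analysed groups. The ICC of change is assumed over 0 to 0.10.

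**Formula.** With *m* analysed per group and all correlation arm-specific, the variance of the arm contrast is inflated by DEFF = 1 + (*m* − 1) × ICC. The true type I error of a nominal 5% test is 2 × [1 − Φ(1.96/√DEFF)], and coverage is its complement. Example: *m* = 5, ICC 0.05 gives DEFF 1.20, 1.96/1.095 = 1.789, type I error 7.4%, coverage 92.6%.

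| Analysed per group | ICC 0 | 0.02 | 0.05 | 0.10 |
|---|---|---|---|---|
| 3 | 5.0% | 5.5% | 6.2% | 7.4% |
| 4 | 5.0% | 5.7% | 6.8% | 8.6% |
| 5 | 5.0% | 5.9% | 7.4% | 9.8% |
| 6 | 5.0% | 6.2% | 8.0% | 11.0% |

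Simulation of week-12 change (7 cycles, two groups per cycle, two-sample t on change) agrees: 5.1 / 5.8 / 7.4 / 9.8% at *m* = 5, and 5.1 / 6.4 / 8.1 / 11.2% at *m* = 6. In a balanced two-visit data set this t-test equals the condition-by-time test of the participant-intercept model.

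**Correlation shared by both arms of a cycle** (for example, virtual against in-person format) cancels in the arm contrast. At *m* = 5 and total within-group correlation 0.02 / 0.05 / 0.10:
- half shared: 5.4 / 6.0 / 6.9%
- all shared: 4.8 / 4.5 / 4.0%, so the intervals are slightly too wide.

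**Cluster-level alternative.** Take the mean change per therapy group, the arm difference within each cycle, and a t-test on the 7 differences (6 df). Its type I error stays near 5% in all these scenarios, including unequal groups of 3 to 6.

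**Its price at 35 per arm, SD 0.67.** The standard error without clustering is √(2 × 0.67²/35) = 0.160.
- SAP-type half-width: 1.995 × 0.160 = 0.32.
- Paired half-width: 2.447 × 0.160 × √DEFF = 0.39 / 0.43 / 0.46 at ICC 0 / 0.05 / 0.10, or 1.22 / 1.34 / 1.45 times as wide.
- Power for 0.40: 55 / 48 / 43%, against a nominal 69%.

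**Can the trial's data reveal clustering?** Hardly. The paired interval is the wider one in about 70% of simulated trials at ICC 0, because of its 6 df, and the narrower one in about 21% at ICC 0.05. At a true ICC of 0.05 the median 95% interval for the ICC runs from −0.13 to 0.48.

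**Limit of the check.** The protocol uses up to four visits. A four-visit simulation gives 7.9% at ICC 0.05 and *m* = 5, but 5.3% when the same lasting effect is not shared between children. Part of that excess is therefore covariance misspecification, and the two-visit figures are the ones to use for clustering.

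**The case against.** The strongest reply is that the size rests on inputs the documents do not supply: the ICC, the group size, the number of groups and the therapist allocation. Several features would keep the ICC low. Both conditions are manualised, fidelity is rated weekly with feedback to lead therapists (5.3), and three of the four weekly doses are given at home (5.1). The trial is a pilot, calls itself potentially underpowered and disclaims definitive conclusions. With about seven groups per arm the ICC cannot be estimated usefully, so a plain limitation statement would do nearly as much as an extra test with 43-55% power.

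Most of this stands, and it sets the severity. Two things remain. The SAP's disclaimer concerns wide intervals, not intervals that are too narrow. And in a pilot without a success rule the estimate and its interval are the main product, so an analysis that holds its level is worth having beside the primary one.

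A reader might go further and infer that the intervals are wrong, or that the false-positive rate nears 15%. The latter needs an ICC of 0.20 with every bit of correlation arm-specific and five per group (14.6%). Nothing in the documents supports that value, and if both arms of a cycle share the correlation the error runs the other way. A reader might also take a wider cluster-level interval as evidence of clustering. Its low degrees of freedom alone produce that in most trials.

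**Conclusion.** The gap is real: treatment is delivered in groups, and the planned model and checks take no account of it. The consequence is conditional. The condition-by-time intervals under-cover only if change is correlated within therapy groups in an arm-specific way. On the stated assumptions (one group per arm per cycle, 7 cycles, 3-6 analysed per group), type I error is about 5.5-6.4% at ICC 0.02, 6-8% at 0.05 and 7-11% at 0.10 when all correlation is arm-specific. With five per group it is about 5.4-7% over the same range when half is shared within cycle, and slightly below 5% when all is shared. There is no error at ICC 0.

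Severity is minor, because no confirmatory decision rests on the result and the ICC is unknown. The documents do not support saying that the intervals are too narrow, only that they may be and that the plan offers no protection against it.

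**What to change.** Keep the SAP model as primary, and add the following before the comparative analysis:

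1. Record therapy group and cycle for each child in the analysis data.
2. For each primary composite, pre-specify the cluster-level analysis of week-12 change: group means, arm difference within cycle, t-test on the cycle differences. Always report it beside the SAP model.
3. State unconditionally that the participant-only intervals assume no within-group correlation and may be too narrow. Do not make this statement depend on a difference between the two intervals or on the estimated ICC.
4. State how many groups each arm forms per cycle, how therapists are allocated, and how a cycle with only one arm is handled.

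A group random effect on post-treatment change should not replace step 2. With about seven groups per arm its variance estimate is at or below zero in about 56% of trials at ICC 0 and 42% at 0.05, and its test is conservative (3.2% and 4.0%).

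The cost is two data fields and one extra analysis per composite; cycle and arm should already be on the randomisation forms. The drawback is a supplementary interval about 1.2 times as wide at ICC 0 and 1.3-1.5 times at ICC 0.05-0.10, at 35 per arm, with lower power. Neither analysis removes confounding if one therapist leads the same arm in every cycle, which is why the allocation should be written down.
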